6.10.3. Additional Analyses of the Primary Outcome

There will be no adjustment for multiple comparisons for additional analyses of the primary outcome, ASAS40.

In the additional analyses of ASAS40, treatment groups of ixekizumab 80 mg Q2W and Q4W will be analyzed without regard to starting dose, unless indicated otherwise.

To support the primary outcome analysis ASAS40 will be analyzed based on the PPS Population for Period 2 at Week 16 (Visit 8) using a logistic regression analysis with treatment, geographic region, number of prior TNF inhibitors used, and baseline CRP status in the model (Section 6.1.1) [de-facto estimand]. Missing data will be imputed using the NRI method (Section 6.3.1).

Additional analyses based on the ITT Population for Period 2 for ASAS40, include:

- Comparisons of each ixekizumab treatment group and placebo at postbaseline visits other than Week 16 (Visit 8) using logistic regression analysis with treatment, geographic region, number of prior TNF inhibitors used, baseline CRP status, in the model (Section 6.1.1) [de-facto estimand]. Missing data will be imputed using the NRI method (Section 6.3.1).

- Comparisons of each ixekizumab treatment group and placebo at Week 16 (Visit 8) and all other postbaseline visits using Categorical MMRM analysis with treatment, geographic region, number of prior TNF inhibitors used, baseline CRP status, visit, treatment-by-visit as fixed factors (Section 6.1.1) [de-jure estimand]
- Comparisons of each ixekizumab treatment group and placebo at Week 16 (Visit 8) and all other postbaseline visits using Fisher's exact test with NRI (Sections 6.1.1 and 6.3.1) [de-facto estimand]

Figures showing the proportion of patients achieving an ASAS40 response at each scheduled visit during Period 2 within each treatment group will be provided.

Time to first ASAS40 response will be assessed based on the ITT Population during Period 2 as described in Section 6.1.1.

Table RHBW.6.5 provides the detailed analyses including analysis type, method and imputation, population, time point, and treatment comparisons for the additional analyses on primary outcome.

6.10.4. Other Secondary Efficacy Analyses

There will be no adjustment for multiple comparisons for other secondary efficacy analyses.

The other secondary efficacy variables for secondary objectives include:

- ASAS40: analyses other than primary analysis (Section 6.10.1) and additional analysis of the primary outcome (Section 6.10.3)
- ASAS20: analyses other than major secondary efficacy analysis (Section 6.10.2)
- ASAS5/6 and partial remission
- Change from baseline in individual components of the ASAS criteria (patient global, spinal pain, function [see BASFI below], inflammation [see BASDAI below], CRP [see CRP below], and spinal mobility [lateral spinal flexion] [see BASMI below])
- Change from baseline in BASDAI: analyses other than major secondary efficacy analysis, 6 individual items and inflammation (mean of Q5 and Q6 on BASDAI)
- BASDAI 50: analyses for other major secondary efficacy analysis (Section 6.10.2)
- Change from baseline in ASDAS: analyses other than major secondary efficacy analysis (Section 6.10.2)
- ASDAS <2.1: analyses other than major secondary efficacy analysis (Section 6.10.2)
- ASDAS inactive disease
- ASDAS disease activity states: inactive disease, low disease activity, high disease activity, very high disease activity, clinically important improvement and major improvement
- Change from baseline in CRP
- Change from baseline in BASFI: analyses other than major secondary efficacy analysis (Section 6.10.2)
- Change from baseline in SPARCC spine score: analyses other than major secondary efficacy analysis (Section 6.10.2)

- Change from baseline in mobility (BASMI linear and individual components, chest expansion, occiput to wall distance)
- Change from baseline in MRI ASSpiMRI –Berlin score
- Change from baseline in enthesitis score (MASES and SPARCC)
- Change from baseline in TJC and SJC
- Incidence of peripheral arthritis by TJC and SJC scores of 46/44 joints
- Incidence rate of anterior uveitis or uveitis flares
- Change from baseline in ASAS-NSAID score (apply to Period 3 analysis only), Section 6.10.4.1.

Treatment comparisons of each ixekizumab treatment group and placebo at Week 16 (Visit 8) and all other postbaseline visits during Period 2 will be provided.

The impact of ixekizumab starting doses will be evaluated for the categorical responses (including ASAS40 and ASAS20) and mean change in continuous efficacy measure of CRP at Week 16 and earlier time point as described in Section 6.1.1.

Descriptive statistics (that is, no inferential testing) will be provided for each treatment group during Period 3, or Combined Periods 2 and 3, as applicable.

Table RHBW.6.5 provides the detailed analyses including analysis type, method and imputation, population, time point, and treatment comparisons for other secondary outcomes.

6.10.4.1. Analyses on NSAID Intake

ASAS-NSAID score is used to present the NSAID (including COX-2 inhibitors) intake by considering the type of NSAID, the total daily dose, and the number of days on which NSAID has been taken during a period of interest (Dougados et al. 2011). Appendix 5 provides the equivalent dose of each NSAID compared to 150 mg diclofenac (Dougados et al. 2011), additional equivalent scores are listed below.

For the NSAID equivalent scoring system, 0 = no intake, 100 = 150 mg diclofenac, 1000 mg naproxen, 200 mg aceclofenac, 400 mg celecoxib, 600 mg etodolac, 90 mg etoricoxib, 200 mg flurbiprofen, 2400 mg ibuprofen, 150 mg indometacin, 200 mg ketoprofen, 15 mg meloxicam, 200 mg nimesulide, 400 mg phenylbutazone, 20 mg piroxicam, 20 mg tenoxicam (Dougados et al. 2011). Additionally, 100 = 180 mg acemetacin, 3600 mg acetylsalicylic acid, 3600 mg salicylic acid, 32 mg lornoxicam, 360 mg loxoprofen, 1000 mg mefenamic acid, 2000 mg nabumetone, 1000 mg niflumic acid, 600 mg tiaprofenic acid, 90 mg pelubiprofen, 240 mg zaltoprofen, 120 mg ketorolac tromethamine (if used intramuscularly [IM] or intravenous [IV]), 40 mg ketorolac (if used orally), 400 mg sulindac, 1200 mg dexibuprofen, 75 mg dexketoprofen, 1110 mg talniflumate. For Vimovo, esomeprazole strontium w/naproxen, esomeprazole w/naproxen and naproxen w/omeprazole, use the score for naproxen; for caffeine with ibuprofen, CAROL-F, and famotidine w/ibuprofen, use the score for ibuprofen; for Dioxaflex Protec and Arthrotec, use the score for diclofenac; for anacin /00141001, use the score for acetylsalicylic acid; for paynocil, use the score for salicylic acid.

The general formula for calculating ASAS-NSAID score is:

(equivalent NSAID score) x (days of intake during period of interest) x (days per week)/(period of interest in days)

A score is assigned depending on the frequency of NSAID use per week (Dougados et al. 2011):

- 7/7: everyday use
- 6/7: 6 days/week
- 4/7: 4 - 5 days/week
- 2/7: 2 - 3 days/week
- 0.5/7: ≤ 1 day/week
- 0: no intake

Using an example in Dougados and colleagues (2011), if during a period of interest (between 2 visits) of 6 months, the patient has taken piroxicam 20 mg during 4 months and if during this 4-month period he has taken piroxicam 3 to 5 days per week, the calculation of ASAS-NSAID is as follows:

$$100 \text{ (20 mg piroxicam score)} \times 120 \text{ (4 months)} \times 4/7 \text{ (3–5 days/ week)} / 180 \text{ (6 months)} = 38.1$$

If the patient has used 10 mg piroxicam during the remaining 2 months on 2 days a week, the NSAID score for this period is:

$$50 \text{ (10 mg piroxicam score)} \times 60 \text{ (2 months)} \times 2/7 \text{ (1 to 3 days/week)} / 180 \text{ (6 months)} = 4.8$$

In this example, the total score for the 6-month period is 42.9 (38.1 plus 4.8).

ASAS-NSAID score will be summarized for the following endpoints at baseline Week 0 (when applicable) and each scheduled visit of interest, which includes the timeframe after the date of previous visit to the date of current visit.

Change from baseline in ASAS-NSAID

- Proportion of patients with 50% decrease in ASAS-NSAID scores compared with baseline
- Proportion of patients with ASAS-NSAID score <10
- Proportion of patients with ASAS-NSAID score = 0

In addition, proportion of patients taking NSAID at specified visit will be summarized.

6.10.5. Sensitivity Analyses

6.10.5.1. pMI

ASAS40, ASAS20, and mean change in ASDAS at Week 16 (Visit 8) will be analyzed based on the ITT Population using the pMI method, as described in Section 6.3.4. Analyses for ASAS40 and ASAS20 will be based on the logistic regression analysis with treatment, geographic region, number of prior TNF inhibitors used, and baseline CRP status in the model (Section 6.1.1).

Analysis for mean change in ASDAS will be based on MMRM analysis. The model will include treatment, geographic region, and number of prior TNF inhibitors used, baseline CRP status,

baseline value, visit, baseline value-by-visit, and treatment-by-visit interaction as fixed factors (Section 6.1.1).

6.10.5.2. Tipping Point Analysis

ASAS40, ASAS20, as well as mean change in ASDAS at Week 16 (Visit 8) will be analyzed based on the ITT Population using the tipping point method (Section 6.3.5).

6.10.5.3. Analysis Including Efficacy Data Post Treatment Discontinuation

Per recommendation in the 2010 National Research Council report *The Prevention and Treatment of Missing Data in Clinical Trials*, additional efficacy data for patients who prematurely discontinued Period 2 are collected during the Post-Treatment Follow-Up Period (Period 4). Patients who discontinue treatment before Week 16 are instructed to schedule a Post-Treatment Follow-Up visit such that the post-treatment data will be collected 16 weeks after initial randomization. The efficacy data of ASAS40 at Week 16 will be summarized by treatment group, but no formal statistical comparison will be performed.

6.10.6. Health Outcomes/Quality-of-Life Analyses

The health outcomes and quality of life (QOL) measures are ASAS HI, SF-36, Fatigue NRS, JSEQ, WPAI-SpA, and QIDS-SR16.

The analyses of health outcomes and QOL measures for Period 2 will be based on the ITT Population. There will be no adjustment for multiple comparisons.

Descriptive statistics will be provided for Period 3 based on the Extended Treatment Period Population.

Table RHBW.6.6 includes the description and derivation of the health outcomes and QOL measures.

Table RHBW.6.7 provides the detailed analyses including analysis type, method and imputation, population, time point, and treatment group comparisons for health outcomes and QOL analyses.

Table RHBW.6.6. Description and Derivation of Health Outcomes and Quality-of-Life Measures

Measure	Description	Variable	Derivation / Comment	Imputation Approach if with Missing Components
ASAS Health Index	The ASAS Health Index (ASAS HI) is a disease specific health-index instrument designed to assess the impact of interventions for SpA, including axSpA. The 17 item instrument has scores ranging from 0 (good Health) to 17 (poor Health) (Kiltz et al. 2013). Each item consists of 1 question that the patient needs to respond to with either “I agree” (score 1) or “I do not agree (score 0).” A score of “1” is given where the item is affirmed, indicating adverse health.	ASAS HI	All item scores are summed to give a total score or index. Range: 0 to 17 0 (good health) and 17 (poor health) Note, items # 7 and #8 may not be applicable for some patients. For those patients who ticked the response “not applicable”, the sum score is analyzed based on n=16 or n=15, respectively.	If ≥4 items (>20%) have missing response, then ASAS HI is missing. If <4 items (≤20%) missing, then imputed sum = sum of scores from nonmissing items x n/ (n - no. of missing items), where n is the total number of applicable items, e.g. 15, 16, or 17. [ASAS Health Index User Manual]
		ASAS HI change from baseline-Major Secondary	Calculated as: observed ASAS HI – baseline ASAS HI	Missing if baseline or observed value is missing
		Proportion of patients with ≥3 improvement from baseline	The smallest detected change of ASAS HI is 3. This variable will only be derived for patients with baseline score ≥3.	Missing if baseline or observed value is missing
		Proportion of patients reaching Good ASAS HI (defined as ASAS HI≤5)	This variable will only be derived for patient with baseline score >5.	Missing if baseline or observed value is missing
Medical Outcomes Study 36-item Short-Form Health Survey	The SF-36 is a 36-item patient-administered measure designed to be a short, multipurpose assessment of health in the areas of physical functioning, role – physical, role – emotional, bodily pain, vitality, social functioning, mental health, and general health. The 2 overarching domains of mental well-being and	8 associated domain scores: • Physical Functioning, • Role Physical, • Bodily Pain, • General Health,	Per copyright owner, the QualityMetric Health Outcomes™ Scoring Software 4.5 will be used to derive SF-36 domain and component scores. After data quality controls, the SF-36 software will re-calibrate the item-level responses for calculation of the domain and component scores. These raw scores will be	Missing data handling offered by SF-36 software will not be used.

Measure	Description	Variable	Derivation / Comment	Imputation Approach if with Missing Components
	physical well-being are captured by the Mental Component Summary and Physical Component Summary scores. The summary scores range from 0 to 100; higher scores indicate better levels of function and/or better health. Items are answered on Likert scales of varying lengths. The SF-36 version 2 (acute version) will be used, which utilizes a 1-week recall period (Ware [2000]).	
 • Vitality • Social Functioning • Role Emotional • Mental Health 2 component Scores: 
 • MCS Score • PCS Score 	transformed into the domain scores (t-scores) using the 1-week recall period. The procedure to derive the SF-36 scores is described in Appendix 6 . It entails exporting the patient data in a CSV or tab-delimited file for import, generation of the SF-36 scores and reports, and export of the calculated scores in a CSV or tab-delimited file for integration into SDTM/ADaM datasets. The summary scores range from 0 to 100.	
		PCS change from baseline-Major Secondary	Calculated as: observed score – baseline score	Missing if baseline or observed value is missing
		MCS and domain scores change from baseline	Calculated as: observed score – baseline score	Missing if baseline or observed value is missing
Fatigue Severity Numeric Rating Scale	The fatigue severity NRS is a patient-administered single-item 11-point horizontal scale anchored at 0 and 10, with 0 representing “no fatigue” and 10 representing “as bad as you can imagine” (Naegeli et al. 2013). Patients rate their fatigue (feeling tired or worn out) by circling the 1 number that describes their worst level of fatigue during the previous 24 hours.	Fatigue Severity NRS	Range: 0 to 10. 0 (no fatigue) and 10 (as bad as you can imagine).	Single item, missing if missing
		Fatigue Severity change from baseline	Calculated as: observed Fatigue Severity NRS – baseline Fatigue Severity NRS	Missing if baseline or observed value is missing
Work Productivity and Activity Impairment Questionnaire—Spondylo-	The Work Productivity Activity Impairment—Spondyloarthritis (WPAI-SpA) consists of 6 questions to determine employment status, hours missed from work because of spondyloarthritis, hours missed from work for other reasons,	Percentage of absenteeism	Percent work time missed due to problem: $(Q2/(Q2 + Q4))*100$	If Q2 or Q4 is missing, then missing
		Percentage of absenteeism - change from baseline	Calculated as: observed value – baseline value	if baseline or observed value is missing, then the value is missing

Measure	Description	Variable	Derivation / Comment	Imputation Approach if with Missing Components
arthritis	hours actually worked, the degree to which spondyloarthritis affected work productivity while at work, and the degree to which spondyloarthritis affected activities outside of work. The WPAI-SpA has been validated in the rad-axSpA patient population (Reilly et al. 2010). Four scores are derived: percentage of absenteeism, percentage of presenteeism (reduced productivity while at work), an overall work impairment score that combines absenteeism and presenteeism, and percentage of impairment in activities performed outside of work. Greater scores indicate greater impairment.	percentage of presenteeism	Percent impairment while working due to problem: $(Q5/10)*100$	If Q5 is missing, then missing
		Percentage of presenteeism - change from baseline	Calculated as: observed value – baseline value	If baseline or observed value is missing, then missing
		Overall work impairment score	Percent overall work impairment due to problem: $(Q2/(Q2+ Q4) + [(1-Q2/(Q2+Q4))*(Q5/10)])*100$	If any of Q2, Q4, or Q5 is missing, then missing
		Overall work impairment score - change from baseline	Calculated as: observed value – baseline value	If baseline or observed value is missing, then missing
		Percentage of activity impairment	Percent activity impairment due to problem: $(Q6/10)*100$	If Q6 is missing, then the value is missing
		Percentage of activity impairment - change from baseline	Change from baseline is calculated as: observed value – baseline value	If baseline or observed value is missing, then missing
		Jenkins Sleep Questionnaire	The Jenkins Sleep Evaluation Questionnaire (JSEQ) is a 4-item scale designed to estimate sleep problems in clinical research. The JSEQ assesses the frequency of sleep disturbance in 4 categories: 1) trouble falling asleep, 2)	JSEQ score

Measure	Description	Variable	Derivation / Comment	Imputation Approach if with Missing Components
	waking up several times during the night, 3) having trouble staying asleep (including waking up far too early), and 4) waking up after the usual amount of sleep feeling tired and worn out. Patients report the numbers of days they experience each of these problems in the past month on a 6 point Likert Scale ranging from 0 = “no days” to 5 = “22-30 days.”	JSEQ score change from baseline	Change from baseline calculated as: observed JSEQ – baseline JSEQ	Missing if baseline or observed value is missing
Quick Inventory of Depressive Symptomatology-self report 16 items	See Section 6.12.6 for description of QIDS-SR16	9 Domains	See Section 6.12.6 for description of each domain	See Section 6.12.6
		Change from baseline in each domain	Calculated as: observed domain score – baseline domain score	Missing if baseline or observed value is missing
		16 Individual items	Range: 0 to 3	Missing if item is missing.
		Change from baseline in each individual item	Calculated as: observed individual item score – baseline individual item score	Missing if baseline or item is missing
		QIDS-SR16 total score	See Section 6.12.6 for description of QIDS-SR16 total score	See Section 6.12.6
		Change from baseline in QIDS-SR16 total score	Calculated as: observed total score – baseline total score	Missing if baseline or observed value is missing

Measure	Description	Variable	Derivation / Comment	Imputation Approach if with Missing Components
		Proportion of patients with at least a 50% decrease in QIDS-SR16 total score	% reduction from baseline calculated as: $100 \times \frac{\text{Baseline} - \text{Observed score}}{\text{Baseline}}$ If the value of % reduction from baseline is ≥ 50 , patients had at least a 50% decrease in QIDS-SR16 total score.	Missing if baseline or observed score is missing

Abbreviations: ASAS = Assessment of Spondyloarthritis International Society; JSEQ = Jenkins Sleep Evaluation Questionnaire; MCS = mental component summary; NRS = numeric rating scale; PCS = physical component summary; SF-36 = Medical Outcomes Study 36-Item Short-Form Health Survey; Q2W = every 2 weeks; Q4W = every 4 weeks; QIDS-SR16 = Quick Inventory of Depressive Symptomatology–Self Report 16 items; SpA = spondyloarthritis; rad-axSpA = radiographic axial spondyloarthritis.

Table RHBW.6.7. Description of Health Outcomes and Quality-of-Life Analyses

Measure	Variable	Analysis Method (Sections 6.1 and 6.3)	Population (Section 6.1.5)	Comparison/Time Point	Analysis Type
36 item Short Form Health Survey (SF-36)	PCS change from baseline – Major Secondary	MMRM	ITT Population	IXE80Q2W & IXE80Q4W vs. placebo at Week 16	Major secondary analysis is MMRM analysis for ITT Population comparing IXE80Q2W & IXE80Q4W vs. placebo at Week 16 (Section 6.10.2).
		MMRM	ITT Population	IXE80Q2W & IXE80Q4W vs. placebo at all other postbaseline visits in Period 2	Health Outcomes/QOL analyses (Section 6.10.6)
		ANCOVA with mBOCF/LOCF	ITT Population	IXE80Q2W & IXE80Q4W vs. placebo at Week 16 and all other postbaseline visits in Period 2	Health Outcomes/QOL analyses (Section 6.10.6)
		Descriptive statistics	Extended Treatment Period Population	No treatment group comparisons during Period 3	Health Outcomes/QOL analyses (Section 6.10.6)
		Descriptive statistics	ITT Population Who are Initially Randomized to Ixekizumab	No treatment group comparisons during Combined Periods 2 and 3	Health Outcomes/QOL analyses (Section 6.10.6)
	MCS, domain scores, change from baseline	MMRM	ITT Population	IXE80Q2W & IXE80Q4W vs. placebo at Week 16 and all other postbaseline visits in Period 2	Health Outcomes/QOL analyses (Section 6.10.6)
		ANCOVA with mBOCF	ITT Population	IXE80Q2W & IXE80Q4W vs. placebo at Week 16 and all other postbaseline visits in Period 2	Health Outcomes/QOL analyses (Section 6.10.6)
		Descriptive statistics	Extended Treatment Period Population	No treatment group comparisons during Period 3	Health Outcomes/QOL analyses (Section 6.10.6)

Measure	Variable	Analysis Method (Sections 6.1 and 6.3)	Population (Section 6.1.5)	Comparison/Time Point	Analysis Type
ASAS Health Index (ASAS HI)	ASAS HI change from baseline - Major Secondary	MMRM	ITT Population	IXE80Q2W & IXE80Q4W vs. placebo at Week 16	Major secondary analysis is MMRM analysis for ITT Population comparing IXE80Q2W & IXE80Q4W vs. placebo at Week 16 (Section 6.10.2).
		MMRM	ITT Population	IXE80Q2W & IXE80Q4W vs. placebo at all other postbaseline visits in Period 2	Health Outcomes/QOL analyses (Section 6.10.6)
		ANCOVA with mBOCF/LOCF	ITT Population	IXE80Q2W & IXE80Q4W vs. placebo at Week 16 and all other postbaseline visits in Period 2	Health Outcomes/QOL analyses (Section 6.10.6)
		Descriptive statistics	Extended Treatment Period Population	No treatment group comparisons during Period 3	Health Outcomes/QOL analyses (Section 6.10.6)
		Descriptive statistics	ITT Population Who are Initially Randomized to Ixekizumab	No treatment group comparisons during Combined Periods 2 and 3	Health Outcomes/QOL analyses (Section 6.10.6)
Proportion of patients with ASAS HI ≥ 3 points improvement from baseline		Logistic regression with NRI; Fisher's exact test with NRI	ITT population With Baseline Score ≥ 3	IXE80Q2W & IXE80Q4W vs. placebo at Week 16 and all other postbaseline visits in Period 2	Health Outcomes/QOL analyses (Section 6.10.6)
		Descriptive statistics	Extended Treatment Period Population With Baseline Score ≥ 3	No treatment group comparisons during Period 3	Health Outcomes/QOL analyses (Section 6.10.6)
Proportion of patients reaching Good ASAS HI (defined as ASAS HI ≤ 5)		Logistic regression with NRI; Fisher's exact test with NRI	ITT population With Baseline Score > 5	IXE80Q2W & IXE80Q4W vs. placebo at Week 16 and all other postbaseline visits in Period 2	Health Outcomes/QOL analyses (Section 6.10.6)

Measure	Variable	Analysis Method (Sections 6.1 and 6.3)	Population (Section 6.1.5)	Comparison/Time Point	Analysis Type
		Descriptive statistics	Extended Treatment Period Population With Baseline Score>5	No treatment group comparisons during Period 3	Health Outcomes/QOL analyses (Section 6.10.6)
Fatigue Severity Numeric Rating Scale	Fatigue Severity change from baseline	MMRM	ITT Population	IXE80Q2W & IXE80Q4W vs. placebo at Week 16 and all other postbaseline visits in Period 2	Health Outcomes/QOL analyses (Section 6.10.6)
		ANCOVA with mBOCF	ITT Population	IXE80Q2W & IXE80Q4W vs. placebo at Week 16 and all other postbaseline visits in Period 2	Health Outcomes/QOL analyses (Section 6.10.6)
		Descriptive statistics	Extended Treatment Period Population	No treatment group comparisons during Period 3	Health Outcomes/QOL analyses (Section 6.10.6)

Measure	Variable	Analysis Method (Sections 6.1 and 6.3)	Population (Section 6.1.5)	Comparison/Time Point	Analysis Type
Work Productivity and Activity Impairment Questionnaire —Spondyloarthritis	Change from baseline in: 
 percentage of absenteeism percentage of presenteeism overall work impairment score percentage of activity impairment 	ANCOVA with mBOCF	ITT Population	IXE80Q2W & IXE80Q4W vs. placebo at Week 16 in Period 2	Health Outcomes/QOL analyses (Section 6.10.6)
		Descriptive statistics	Extended Treatment Period Population	No treatment group comparisons during Period 3	Health Outcomes/QOL analyses (Section 6.10.6)
JSEQ	JSEQ score change from baseline	MMRM	ITT Population	IXE80Q2W & IXE80Q4W vs. placebo at Week 16 and all other postbaseline visits in Period 2	Health Outcomes/QOL analyses (Section 6.10.6)
		ANCOVA with mBOCF	ITT Population	IXE80Q2W & IXE80Q4W vs. placebo at Week 16 and all other postbaseline visits in Period 2	Health Outcomes/QOL analyses (Section 6.10.6)
		Descriptive statistics	Extended Treatment Period Population	No treatment group comparisons during Period 3	Health Outcomes/QOL analyses (Section 6.10.6)
Quick Inventory of Depressive Symptomatology-self report 16 items (QIDS-SR16)	Change from baseline in QIDS-SR16 total score, the 9 QIDS-SR16 domains and 16 individual item	ANCOVA with mBOCF	ITT Population ITT Population with moderate depression at baseline (QIDS-SR 16 total score ≥ 11)	IXE80Q2W & IXE80Q4W vs. placebo at Week 16	Health Outcomes/QOL analyses (Section 6.10.6)
		Descriptive statistics	Extended Treatment Period Population Extension Period	No treatment group comparisons during Period 3	Health Outcomes/QOL analyses (Section 6.10.6)

Measure	Variable	Analysis Method (Sections 6.1 and 6.3)	Population (Section 6.1.5)	Comparison/Time Point	Analysis Type
			Population with moderate depression at baseline (QIDS-SR 16 total score ≥ 11)		
	Proportion of patients with at least a 50% decrease in QIDS-SR16 total score	Logistic regression with NRI; Fisher's exact test with NRI	ITT Population for patients with moderate depression at baseline (QIDS-SR16 total score)	IXE80Q2W & IXE80Q4W vs. placebo at Week 16	Health Outcomes/QOL analyses (Section 6.10.6)
		Descriptive statistics with NRI	Extension Period Population with moderate depression at baseline (QIDS-SR 16 total score ≥ 11)	No treatment group comparisons during Period 3	Health Outcomes/QOL analyses (Section 6.10.6)

Abbreviations: ANCOVA = analysis of covariance; ASAS = Assessment of Spondyloarthritis International Society; IXE80Q2W = ixekizumab 80 mg every 2 weeks; IXE80Q4W = ixekizumab 80 mg every 4 weeks; ITT = intent-to-treat; JSEQ = Jenkins Sleep Evaluation Questionnaire; mBOCF = modified baseline observation carried forward; LOCF = last observation carried forward; MCS = mental component summary; MMRM = mixed-effects model of repeated measures; NRI = nonresponder imputation; PCS = physical component summary; QOL = quality of life; QIDS-SR16 = Quick Inventory of Depressive Symptomatology–Self Report 16 items.

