**8.1.2.17. Work Productivity and Activity Impairment Questionnaire–Spondyloarthritis**

The WPAI-SpA consists of 6 questions to determine employment status, hours missed from work because of SpA, hours missed from work for other reasons, hours actually worked, the degree to which SpA affected work productivity while at work, and the degree to which SpA affected activities outside of work. The WPAI-SpA has been validated in the rad-axSpA patient population (Reilly et al. 2010). Four scores are derived: percentage of absenteeism, percentage of presenteeism (reduced productivity while at work), an overall work impairment score that combines absenteeism and presenteeism, and percentage of impairment in activities performed outside of work. Greater scores indicate greater impairment (Reilly Associates [WWW]).

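### The WPAI-SpA overall work impairment score is set to missing when Q5 is blank, even where zero hours worked already fixes it at 100%

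*SAP*

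**What the plan says.** Table RHBW.6.6 (SAP 6.10.6) derives the scores from the numbered WPAI-SpA items:

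- **Absenteeism** = 100 × Q2/(Q2 + Q4). Missing-data rule: "If Q2 or Q4 is missing, then missing".
- **Presenteeism** = 100 × Q5/10, missing if Q5 is missing.
- **Overall work impairment** = 100 × {Q2/(Q2 + Q4) + [1 − Q2/(Q2 + Q4)] × Q5/10}. Missing-data rule: "If any of Q2, Q4, or Q5 is missing, then missing".
- **Activity impairment** uses Q6 alone.

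Change from baseline in each score needs both the baseline and the later value.

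Protocol 8.1.2.17 describes the fifth item as "the degree to which SpA affected work productivity while at work". It lists hours missed because of SpA separately from hours missed for other reasons.

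In Period 2 the Schedule of Activities (Protocol Appendix 2) places the WPAI-SpA at Week 0 and Week 16, and also at the early termination visit. Table RHBW.6.7 analyses change at Week 16 by ANCOVA with mBOCF in the ITT population. SAP 6.10.6 applies no multiplicity adjustment to these outcomes.

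**The concern.** Q5 asks about impairment during work. A patient who worked no hours in the recall period has nothing to rate and may well leave it blank. The rule treats that blank as lost information, although the overall score does not depend on Q5 in that situation.

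Any score lost by this route is at the top of the scale, so the loss is related to the outcome. At Week 16 it could distort the comparison between arms if zero-hours absence with Q5 blank is more frequent in one arm. At Week 0 it removes patients who were off work at entry, including any who had returned by Week 16.

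**Working it through.** **Inputs.** The formulas and missing-data rules come from Table RHBW.6.6, the item descriptions from Protocol 8.1.2.17, and the mBOCF definition from SAP 6.3.2. The plan states no figure to reproduce here.

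**1. Algebra.** Put Q4 = 0 and Q2 > 0. Then Q2/(Q2 + Q4) = 1, and the Q5 term is multiplied by 1 − 1 = 0. The score is 100 × (1 + 0) = 100 for every Q5.

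**2. Numbers.**

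| Q2 (h) | Q4 (h) | Q5 = 0 | Q5 = 5 | Q5 = 10 |
|---|---|---|---|---|
| 40 | 0 | 100 | 100 | 100 |
| 8 | 0 | 100 | 100 | 100 |
| 1 | 0 | 100 | 100 | 100 |
| 39 | 1 | 97.5 | 98.75 | 100 |
| 36 | 4 | 90 | 95 | 100 |
| 20 | 20 | 50 | 75 | 100 |

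Once any hours are worked, Q5 matters and the present rule is sound. With Q2 = Q4 = 0 the formula is 0/0, so the score is undefined and should be missing.

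**3. One patient, four scores.** Take Q2 = 40, Q4 = 0, Q5 blank. Absenteeism is 100%. Presenteeism is missing, as it should be. Overall impairment is missing, although its value is known. Activity impairment is scored from Q6. The patient is fully absent on one score and has no value on the score that combines absence with impairment at work.

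**4. Does imputation restore it?** mBOCF as defined in SAP 6.3.2 carries values forward for patients who stop study drug. A randomized patient with no post-baseline observation is left out unless treatment stopped for an adverse event. A patient still on treatment at Week 16 with Q5 blank has no post-baseline overall score in Period 2 and drops out of the analysis. Collection at the early termination visit does not help that patient.

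**5. Illustration of size, on assumptions not in the documents.** Let a share p of workers at a visit have Q4 = 0, Q2 > 0 and Q5 blank, and let the other workers average m. Including the group at 100% gives a mean of (1 − p)m + 100p, so leaving it out lowers the visit mean by p(100 − m).

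- p = 2%, m = 70: 0.02 × 30 = 0.6 points.
- p = 5%, m = 50: 0.05 × 50 = 2.5 points.
- p = 10%, m = 30: 0.10 × 70 = 7.0 points.

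For the raw difference between arms at Week 16, with the same m in both arms, the shift is (p for placebo − p for ixekizumab) × (100 − m):

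- 6% against 2%, m = 45 to 35: 0.04 × 55 = 2.2 to 0.04 × 65 = 2.6 points.
- 8% against 2%, m = 45 to 35: 0.06 × 55 = 3.3 to 0.06 × 65 = 3.9 points.
- Equal shares: no shift.

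These are differences in raw Week 16 level. The planned analysis is of change from baseline with the baseline value in the model. A patient off work at both visits would contribute a change of 100 − 100 = 0, so the figures above probably overstate the effect on the planned estimate.

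**The case against.** Several points count against giving this much weight, and most of them stand.

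- **Blankness is inferred.** Neither document reproduces the questionnaire or a skip instruction. Protocol 10.2.1 says patient questionnaires are entered on a tablet, but nothing says whether Q5 can be left empty. A patient who enters any Q5 value is scored 100% and kept. A reader might infer that the most impaired workers are dropped as a matter of course; the documents support that only if Q5 is blank.
- **Q4 = 0 with Q2 > 0 need not mean a week lost to SpA.** Hours missed for other reasons do not enter the formula. Someone who lost one hour to SpA and spent the rest of the week on leave also scores 100%. That is a feature of the existing formula, which already gives this patient 100% when Q5 is answered; the correction only applies it consistently.
- **Loss at Week 0 is not bias between arms.** It arises before treatment and is balanced in expectation by randomization.
- **The numbers are assumed.** The documents give no employment or absence rates. With about 100 patients per arm and only workers scored, 6% against 2% is at most 6 patients against 2.
- **The absence itself is still analysed**, through the absenteeism score.

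None of this explains why a score that Q2 and Q4 fully determine should be set to missing.

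**Conclusion.** The point holds in conditional form. For Q4 = 0 and Q2 > 0 the overall score is exactly 100% by the SAP's own formula, and the stated rule discards it if Q5 is blank. No other part of the readable documents restores it for a patient still on treatment.

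A reader might go further and conclude that the Week 16 comparison is biased toward no difference by some 2 to 4 points. The documents do not support that. It would need more such absence on placebo, Q5 blank in those patients, and the assumed rates above, and it rests on raw levels instead of the planned baseline-adjusted change. What can be said is that the comparison could be biased if this loss at Week 16 differs by arm, and that loss at Week 0 reduces precision and narrows the analysed population. The actual size is unknown.

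One of the four WPAI-SpA scores is affected, as an other-secondary outcome without multiplicity control. No primary or major secondary result changes. This is a small improvement to a derivation rule.

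**What to change.** In Table RHBW.6.6, replace the missing-data rule for overall work impairment with:

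- If Q4 = 0 and Q2 > 0, the score is 100% at every visit, regardless of Q5.
- Otherwise, the score is missing if Q2, Q4 or Q5 is missing.
- If Q2 = Q4 = 0, the score stays missing.

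Presenteeism stays missing when Q5 is missing. The change from baseline then follows from the corrected scores.

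The cost is a sentence in the SAP, one derivation line and a rerun of this score. No new data are needed. A count by arm and visit of patients with Q4 = 0, Q2 > 0 and Q5 blank would show how much the rule mattered.

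Timing needs openness. The SAP's revision history places first unblinding in June 2018, after Version 3, and Version 4 in February 2019, before the Week 52 lock. A revised Week 16 result would therefore follow unblinding. Protocol 9.2 gives the route: describe the change and its justification in the clinical study report. The justification comes from the formula alone and does not depend on any result.
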